 capsule at night for the first 2 weeks, and then two capsules of the placebo at night for
 the remaining 4 weeks.

Blinding

This study will include a placebo. Study participants and providers will be blinded to which treatment they are receiving (placebo or LDN). Keefer's Compounding Pharmacy will create a placebo and compound the study medication into a 2 mg dose capsule. The NorthShore pharmacy will then place 70 capsules of placebo or study medication in moisture tight, light-resistant prescription bottles with appropriate labeling. When a participant enrolls, the pharmacy will provide the prescription bottle with the correct pills (either placebo or study medication) for the research personnel to pick up from the NorthShore pharmacy and give to the participant. This will ensure the trial remains double-blinded.

Randomization

The randomization will be done by statistician prior to initiation of the study, and will be kept with the pharmacy. Once a participant is enrolled, a call will be made to the pharmacy who will supply the correct medication, either the LDN or placebo, to maintain blinding.

Indication and patient population

LDN has demonstrated amelioration of symptoms in conditions associated with interstitial/painful bladder syndrome. The proposed mechanism of action of LDN in animal studies suggests that neuroinflammation is reduced, opioid signaling is upregulated thus increasing the sensitivity of signaling, and endogenous opioids are increased, including beta-endorphins, which have anti-inflammatory properties and may produce neuropsychological benefits. IC/PBS is a poorly understood syndrome, characterized by pain and likely inflammation with several treatment modalities that are either not effective, time consuming or have adverse risks associated with them.

Sample Size:

Using a randomized double-blinded design, we estimate that a sample size of 22 patients in each group (total N=44) will achieve an 80% statistical power to detect a minimum 30% reduction in pain symptoms for LDN over placebo group when using an alpha of 0.05.

Duration and Number of Sites

Enrollment will begin following approval by the IRB in the spring of 2020, and patient participation will last for six weeks. Patients diagnosed with IC/PBS by urogynecology providers at the Center for Pelvic Health in the NorthShore University HealthSystem will be eligible to participate.

Study Population

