After two weeks, participants will be contacted by research personnel by phone to check to see that they completed the 24-hour bladder diary, to make sure they are taking the medication, and to ask about any adverse effects from the study medication. If adverse effects are noted, study personnel will attempt to trouble shoot. For example, the most commonly reported adverse effect is vivid dreams. If study participants experience this, they will be encouraged to try taking the medication in the morning. If study participants have not completed the 24 bladder diary, they will be encouraged to do so as soon as possible.

At the completion of the six weeks, patients will return to the office for:

- A provider appointment to discuss additional therapeutic options for treatment of IC/PBS
- 2. Vital sign assessment including blood pressure
- 3. Blood collection for study exit hepatic panel
- 4. Complete study questionnaires
 - a. Interstitial Cystitis Symptom Index
 - b. Interstitial Cystitis Problem Index
 - c. Pelvic pain and urgency/frequency patient symptom scale (PUF)
 - d. Visual Analog Scale
 - e. Medical Outcomes Study Short Form 36 (SF-36)
 - f. Study completion and tolerability survey
- 5. Return unused study medication
- 6. Provide two completed 24-hour bladder diaries
 - a. One performed prior to starting the medication

- b. One performed at completion of the study last day
 - i. Participants will be given instructions about completing this on the last day of taking study medication, or the day after completion of all study
- 7. This concludes their participation in this research study

Study drug and comparator

Drug shipment/receipt: The medication will be compounded by Keefer's pharmacy into 2mg capsules. The medication will be shipped to the Skokie inpatient pharmacy.

Drug packaging: Keefer's pharmacy will be asked to supply 1,540 capsules of the study medication and placebo, which is enough for twenty-two study participants. Seventy capsules of medication and identical placebo will be placed into separate but identical moisture tight and light-resistant amber vials by the NorthShore pharmacy with specific lot numbers and expiration dates as determined by Keefer's pharmacy.

Drug storage: The medication will be stored at the NorthShore Skokie inpatient pharmacy in tight, light-resistant containers. The Beyond-Use-Date (BUD) for this nonaqueous formulation of low-dose naltrexone HCl capsules will be labeled as six months.

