Drug preparation: The LDN study medication and placebo will be compounded and prepared by Keefer's pharmacy.

Drug dispensing and accountability: The medication will be dispensed by the Skokie NorthShore pharmacy to the research personnel to provide to the participant. Participants will return their pill vial, including any unused medication at the time of their six-week follow up visit. Any residual medication will be documented, and the medication returned to the pharmacy for disposal by onsite destruction.

Drug administration: the patients will take their appropriate randomized medication for a total of six weeks. The first two weeks, patients will take one capsule at night, and for the last four weeks, they will take two capsules at night.

Contraindications/concomitant medications: Absolute contraindications to taking LDN include pregnancy, moderate-severe alcohol use disorder, and opioid dependence. In the case reports and small randomized trials, LDN does not appear to interfere with other medications patients were taking at the time of the study.

Breaking the blind: In the event of an adverse event, a phone call can be made to the NorthShore Skokie inpatient pharmacy to determine if they are taking the study medication or placebo. If this should occur, the phone call should be followed up with written documentation in the form of an email with notification of the break in the blind.

Drug destruction: Study participants will be requested to return the pill vials to clinic. Any residual medication will be documented, and the medication returned to the pharmacy for disposal by onsite destruction.

Medication compliance assessment: Study participants will be requested to return the pill vials to clinic. Any residual medication will be documented, and the medication returned to the

pharmacy for disposal by onsite destruction. Participants will also be asked to keep a log of when they take their medication.

Safety Assessment

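### Vials carry lot numbers and expiry dates set by the compounding pharmacy, and nothing says these are masked or common to both arms; if they are product-specific, staff could group vials by arm

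*Combined protocol and SAP*

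**What the plan says.** The drug packaging paragraph (under study drug and comparator) makes the containers look alike: "Seventy capsules of medication and identical placebo will be placed into separate but identical moisture tight". It then adds that they are "light-resistant amber vials by the NorthShore pharmacy with specific lot numbers and expiration dates", which the compounding pharmacy sets. The Blinding section describes the same containers only as "moisture tight, light-resistant prescription bottles with appropriate labeling". Neither place mentions a kit number, a masked lot code or a common expiry date.

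The drug storage paragraph dates the active product: "The Beyond-Use-Date (BUD) for this nonaqueous formulation of low-dose naltrexone HCl capsules will be labeled as six months". No beyond-use date is given for placebo.

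On handling, the Blinding section has the pharmacy supply each bottle "for the research personnel to pick up from the NorthShore pharmacy and give to the participant", and concludes: "This will ensure the trial remains double-blinded". The dispensing and accountability paragraph closes the loop: "Participants will return their pill vial, including any unused medication at the time of their six-week follow up visit". The paragraph on breaking the blind lets a telephone call to the hospital pharmacy reveal a participant's allocation after an adverse event. It states no severity threshold, and asks for a follow-up email without naming its recipients.

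**The concern.** A lot number exists to identify a batch of one product. If it appears on otherwise identical vials, it can sort them into two groups for anyone who sees enough of them. The allocation list is held by the pharmacy to protect the blind, but a visible lot code could let one known allocation stand for many.

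Both primary outcomes, the Interstitial Cystitis Symptom Index and the pain visual analogue scale, are self-reported. Adverse effects and tolerability are secondary outcomes. Research personnel deliver the vials, ask about adverse effects in the two-week call, and may withdraw participants at their discretion. Staff who know or suspect the arm could coach, probe or withdraw participants differently, and could shape what participants expect. Bias of that kind cannot be removed in the analysis.

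The issue is separate from who may request a code break and when: even a fully justified break would spread through a shared lot.

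**Working it through.** **1. Supply.** The treatment schedule gives 14 nights × 1 capsule + 28 nights × 2 capsules = 70 capsules per participant. For 22 participants, 22 × 70 = 1,540, which reproduces the figure in the drug packaging paragraph exactly. Read as 1,540 capsules of each product, this covers 22 per arm and all 44 participants. One lot per product for the whole trial is therefore possible.

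**2. Is one lot per product certain?** No. Six months is about 26 weeks and a course lasts 6 weeks, so a vial must be handed out within about 26 − 6 = 20 weeks of compounding to be finished in date. The protocol gives no recruitment period. If recruitment runs beyond about 20 weeks from compounding, further lots are needed.

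**3. Do the identifiers differ between arms?** The documents do not say. Different lot numbers are the ordinary case for two separately compounded products, and a shared number would need an arrangement that is not described. Different expiry dates are less certain, because both products come from the same compounder and could be made and dated together. Different lot numbers alone would be enough for grouping.

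**4. Reach of one code break, if lots are product-specific and visible.** Assume L equal lots per product, used one after another, with both products changing lots together. Vials sharing the revealed lot = 22 / L. Adding the other product's concurrent lot by elimination gives 44 / L.

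| Lots per product (L) | Same lot, 22/L | With concurrent other lot, 44/L |
|---|---|---|
| 1 | 22 | 44 |
| 2 | 11 | 22 |
| 4 | 5.5 | 11 |

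These are upper limits. Participants who have finished the six-week visit have already given their outcomes. With one lot per product and 22 participants already finished, for example, at most 44 − 22 = 22 still have outcomes at risk. If the label code is common to both products or masked, the reach is zero.

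**5. How likely is any code break?** The documents give no rate. Assume a probability q per participant, independent across 44 participants. The chance of at least one break is 1 − (1 − q)^44:

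- q = 1%: 36%
- q = 2%: 59%
- q = 5%: 90%
- q = 10%: 99%

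These values of q are illustrative. They show only that a break somewhere in the trial is not remote, even at a low rate per participant.

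**The case against.** The strongest reply is that the plan never says the lots or dates differ. One compounder makes both products and could date them together. The vials are described as identical, and the Blinding section's phrase about labelling could cover a masked label. This stands to the extent that the plan cannot be said to unblind anyone. It does not close the gap: the only label content the plan specifies is lot and expiry, and no safeguard is described for either.

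Four stronger readings are tempting, and the documents do not support them.

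- A reader might infer that participants could also sort vials. Each participant receives one bottle and has nothing to compare it with.
- A reader might infer that one code break always exposes all 44. That needs product-specific codes, one lot per product throughout, and a break early enough that nobody has completed.
- A reader might infer that staff could identify an arm without any code break, by linking vivid dreams to a lot. The background section reports 37% from a 12-week fibromyalgia crossover but no placebo rate, and a dream report does not identify an arm. Dreams can hint at an individual's allocation whatever the label says.
- A reader might infer that the same individuals deliver vials, make the two-week call and receive returns. The protocol assigns the first two tasks to research personnel as a group, and says only that returns come to the clinic at the six-week visit.

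Two further points are fair. The two-week call is by telephone, with no vial in view, and the primary outcomes are completed by the participant, so staff do not rate them. Staff influence would therefore be indirect, and the documents establish neither its size nor its direction.

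Finally, the Blinding section names participants and providers as blinded, not research personnel. But it routes vials through those personnel as part of the procedure said to preserve the blind, so they are evidently meant not to know the arm.

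**Conclusion.** The point holds in conditional form. As written, the labelling rule puts potentially product-specific identifiers on vials that research personnel handle across participants, and nothing masks them. The claim that the procedure ensures double-blinding is therefore not secured; the documents do not show that it fails.

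If lots are product-specific, one code break reaches at most 44 participants with one lot per product, about 22 with two and about 11 with four, less those who have already completed. If the code is common or masked, it reaches none through the label. The conclusion rests on two assumptions that the documents neither state nor exclude: that lots or dates differ by product, and that the label shows them to staff. The first is likely for lot numbers and only possible for expiry dates. The second is the natural reading of the drug packaging paragraph. The change is worth making because it is cheap and protects the blind under any of these readings.

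**What to change.** Revise the drug packaging paragraph so that each dispensed vial carries only the participant or kit number and a single expiry date common to both arms, namely the earlier of the two products' dates. State that lot numbers and product-specific dates are kept only in the hospital pharmacy's accountability log, cross-referenced to the kit number and not visible to research personnel or providers. Refer to this rule in the Blinding section in place of the general phrase about labelling.

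If the pharmacy already works this way, a sentence or two saying so is enough. Otherwise the cost is a label change and a cross-reference in the log. The downsides are that lot tracing must run through the pharmacy log, and that some capsules may be discarded early when the common date falls before their own.

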In low doses, naltrexone acts as a neuroprotective glial modulator by inhibiting activation of microglia, which are central nervous system immune cells, activated by various stressors. Upon activation, they produce inflammatory and excitatory molecules, resulting in a pro-inflammatory cascade, leading to neurotoxicity. Naltrexone specifically binds as an antagonist to Toll-like receptor 4 (TRL4). TLR4 has downstream cellular signaling leading to pro-inflammatory cytokines including interlukin-1, tumor necrosis factor-alpha, interferon- beta, excitatory amino

acids, substance P, and nitiric oxide, resulting in neuroinflammation, (23, 24, 25, 29, 31). TLR4 is expressed in the lower urinary tract of both humans and mice (36). LDN also plays a role in modulating the neuroimmune axis by its action on maturation of dendritic cells and in mitochondrial apoptosis (23).

LDN also upregulates opioid signaling by intermittent blockade of opioid receptors for 4-6 hours, creating a rebound effect, increasing endogenous opioids (22) and upregulates opioid signaling, by increasing the production of opioid receptors. (25) One of the endogenous opioids increased, beta-endorphins, is known to have anti-inflammatory properties (23, 24). The increased production of endogenous opioids may also inhibit the proliferation of B and T lymphocytes, and modulate the immune system (23, 25). Furthermore, upregulated endorphins may produce neuropsychological benefits (29).

Some adverse effects have been reported with the use of LDN. Vivid dreams, nightmares and insomnia are possible side effects, which can be mitigated by changing drug administration from bedtime to morning (23), and do improve with longer duration of taking LDN (34). There is also a reduction in pain relief from narcotics for at least six to 24 hours after taking low-dose naltrexone. In addition, low-dose naltrexone should not be used in patients who are currently receiving opioid analgesics. Naltrexone is designed to suppress cravings for opioid and alcohol use. Individuals with moderate to severe alcohol use disorder who take naltrexone may experience withdrawal symptoms if they stop drinking than can be potentially fatal due to the development of seizures. Individuals who use opioid pain medication and take naltrexone will not have the same pain relief, and may take more medication to overcome this, resulting in a potentially fatal overdose.

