Patients taking thyroid replacement may require a lower amount of thyroid medication and should have thyroid function tests performed regularly. Elevation of liver enzymes is a potential risk with naltrexone treatment, but is not felt to be common with low-dose therapy. Other potential side effects may include but are not limited to gastrointestinal disturbances, such as stomach cramps and diarrhea (24, 26, 35), agitation, anxiety, flu-like symptoms, and headaches. One case report reported increased yawning, dry mouth, and thirst (35). The effect of naltrexone on the menstrual system has had mixed results, with some studies reporting no differences (51, 52), while one study noted an increase in pulsatile luteinizing hormone and prolactin secretion (53). No studies with low-dose naltrexone have explored changes in the menstrual cycle.

Low-dose naltrexone should be compounded with short-acting fillers, and calcium carbonate should be avoided. LDN should be stopped at a minimum of 24 hours prior to the time narcotics may be needed for pain relief for a scheduled surgical procedure (24, 26). Absolute contraindications include pregnancy and opioid dependence. (23)

Summaries of studies conducted to date

There have been no studies investigating the efficacy of using LDN in the treatment of IC/PBS to date. Studies have shown benefit in helping to relieve pain in patients with fibromyalgia(38, 42), complex regional pain syndrome (40) and chronic low-back pain (38). These conditions are commonly associated with IC/PBS. Studies with LDN have also demonstrated improvement in disease activity in autoimmune conditions like inflammatory bowel disease and multiple sclerosis(22, 24, 25, 29, 30, 31, 32, 33). There is also evidence that LDN may enhance emotional

well-being (25, 34), life-satisfaction (34), and may be beneficial in some dermatologic conditions (29, 41).

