A pilot study of eight women who participated in a 10 week, single-blind, crossover study of the immune effects of LDN in women with fibromyalgia noted improvement in fibromyalgia associated pain, along with reduction in known inflammatory plasma marks that was significant from baseline. Of these eight women, two experienced adverse effects from pre-existing conditions (32). In an open-label study of 42 patients with irritable bowel syndrome who took 0.5mg LDN for four weeks, overall symptom relief was seen in 76% of the patients, and there was an increase in pain-free days. Two adverse events possibly related to LDN were observed: stomatitis and mild allergic dermatitis (46).

A pilot study with forty patients with primary progressive multiple sclerosis was performed to assess the safety and tolerability of six months of LDN. Five of the forty patients left the study due to one episode of enuresis, worsening neurologic complaints, increased bilirubin, urinary tract infection leading to renal failure, and opioid use during the study (45). Overall, the medication was well tolerated.

A double-blind, placebo-controlled, crossover study of 31 women with fibromyalgia were treated with LDN for twelve weeks and placebo for four weeks. There was a significant reduction in pain score between the LDN and placebo. Reported adverse effects were of vivid dreams (37%) and headache, and these were more significant in the LDN group (42)

A pilot study was done to examine the effectiveness of LDN in reducing the symptoms of fibromyalgia. Overall symptom severity was significantly reduced in the drug condition, as contrasted to baseline and placebo conditions. In the entire group of participants, LDN reduced fibromyalgia symptoms by 30.2% over placebo. Specific symptoms, including average pain, highest pain, fatigue, and stress, were also significantly impacted by the drug. The observed effects were accompanied by a very low incidence of side effects, suggesting LDN may be an effective and well-tolerated treatment option for individuals with fibromyalgia. (44)

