Patients diagnosed with IC/PBS by one of the urogynecology providers at the Center for Pelvic Health in the NorhShore University HealthSystem by diagnostic criteria for IC/PBS by AUA guidelines will be eligible to participate. A patient must then meet all applicable inclusion and exclusion criteria.

Inclusion criteria

- 1. Patients aged eighteen and older
- 2. Meet criteria for IC/PBS as defined by the American Urology Association as "an unpleasant sensation (pain, pressure, discomfort) perceived to be related to the urinary bladder, associated with lower urinary tract symptoms or more than six weeks duration, in the absence of infection or other identifiable causes" (8)

- 3. Newly diagnosed and treatment naïve for IC/PBS or previously diagnosed with IC/PBS, but who have no received treatment in the past four weeks. Patient who use anti-inflammatory medication on an as needed basis in the four weeks prior to the study will be included.
- 4. Have had a cystoscopy in the last 6 months prior to study entry to rule out confounding conditions
- 5. English speaking
- 6. Working telephone number
- 7. Able to attend research visits

Exclusion criteria:

- 1. Patients under the age of 18
- 2. Patients with known liver disease, including total bilirubin >1.2, AST> 32, ALT> 54 within the last six months or with enrollment screening testing
- 3. Patients with known kidney disease
- 4. Patients who have thyroid disease and who are taking thyroid replacement medications
- 5. Patients with known neurologic disease affecting bladder function
- 6. Patients with known bladder or urethral cancer
- 7. Patients with bladder, urethral, or ureteral calculi
- 8. Patients who have had a positive urine culture or a clinical UTI in the past 6 weeks
- 9. Patients who are currently pregnant or breast feeding (15)
- 10. Patients who are actively using opioid analgesics
- 11. Patients with moderate-severe alcohol use disorder
- 12. Patients who are actively using sleep aids
- 13. Patients who are regularly using anti-inflammatory medications, such as daily Celebrex for arthritis. Those who use an anti-inflammatory medication on an as needed basis may use the medication prior to enrollment in the study.
- 14. Patients who have had a known adverse reaction to naltrexone
- 15. Patients who are acutely ill
- 16. Patients who are diagnosed with a significant psychological comorbidity that would interfere with study participation (32)

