Adverse Experiences (AEs): Study participants will be asked to document any adverse experiences or events they experience while participating in the study. The National Cancer Institute Common Terminology Criteria for Adverse Events (CTCAE) version 5.0 will be used for adverse event reporting. The CTCAE describes an adverse event as "any unfavorable and unintended sign, symptom, or disease temporally associated with the use of a medical treatment or procedure that may or may not be considered related to the medical treatment or procedure."

Documentation of AEs: All AEs experienced by study participants will be documented in the collaboration portal.

Coding of AEs: AEs will be given a grade according to the CTCAE version 5.0

Serious Adverse Events

Definition: Serious AEs will be given a grade according to the CTCAE version 5.0

Reporting: Serious AEs will be documented in writing

Expected AEs/toxicities: To date, there are no reports of interactions between LDN and other medications. The sample size of these studies is small, and there are likely a large number of interactions that have yet to be tested (39). Other trials have reported vivid dreams (34), nausea, epigastric pain, mood alteration, mild irritability, headache, and joint pain. (43)

Unplanned visits: Study participants will be encouraged to contact research personnel with any questions or concerns they have about the medication or the study. If study personnel determine the patient needs a clinic visit, the patient will be seen by a provider, and that visit will be documented in Epic as a medical visit. The visit will also be included in the patient's research documentation.

Subject Completion and Early Withdrawal Procedures for completion

Upon completion of the six-week study period, participants will have an appointment with their physician to discuss additional treatment options for IC/PBS. At that visit, study participants will complete study forms and submit two 24-hour bladder diaries, and have a blood sample collected. They will receive \$50 in compensation. In the event that study participants are unable to complete the study, they will receive a prorated compensation of \$20 in the form of a gift card.

Procedures for early withdrawals:

Patients will be free to withdrawal for any reason or if deemed necessary by research staff or any other medical provider.

Reasons for withdrawals:

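### The safety section reports no LDN drug interactions although the protocol describes one with opioids, and the visible text has no specific rule for an opioid started during treatment

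*Combined protocol and SAP*

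**What the plan says.** The statement at issue stands under Safety Assessment, Expected AEs/toxicities: "To date, there are no reports of interactions between LDN and other medications". The next sentence adds that the studies were small and that many interactions probably remain untested. Under Study drug and comparator, the paragraph on contraindications and concomitant medications lists opioid dependence as an absolute contraindication. It then says that in case reports and small randomized trials LDN has not seemed to interfere with participants' other drugs.

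Background and Significance reads differently:

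- On opioids: "There is also a reduction in pain relief from narcotics for at least six to 24 hours after taking low-dose naltrexone", and "low-dose naltrexone should not be used in patients who are currently receiving opioid analgesics".
- On overdose: people who use opioids and take naltrexone may take more opioid to regain relief and could die of an overdose. The warning is repeated under Evaluation of benefits, risks and discomforts. Neither place specifies the low dose.
- On thyroid drugs: "Patients taking thyroid replacement may require a lower amount of thyroid medication".
- On planned procedures: "LDN should be stopped at a minimum of 24 hours prior to the time narcotics may be needed for pain relief". This is background advice, not a trial procedure.

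The entry criteria act on this. Exclusion 10 reads "Patients who are actively using opioid analgesics", exclusion 4 reads "Patients who have thyroid disease and who are taking thyroid replacement medications", and exclusion 21 removes people with already scheduled procedures that need analgesia.

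**The concern.** Staff look to the expected-toxicity text when a participant calls about another drug. Read alone, it tells them that no interaction is known. The same protocol treats concurrent opioids as something to avoid and describes a route from reduced relief to overdose.

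The second half of the concern is what happens after dosing begins. The trial enrolls people with a painful condition, so an opioid for a flare, an injury or emergency care is foreseeable. If the text gives no specific instruction, the default is that study drug continues alongside an opioid, which the protocol says should not happen. At stake is the safety of an occasional participant, not the treatment comparison.

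**Working it through.** No figure in the plan is in dispute, so the check is a reading of the relevant sections against each other.

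**Step 1: do the statements conflict?**

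| Topic | Safety Assessment | Background and Significance | Conflict? |
|---|---|---|---|
| Opioids | No interaction reported | Relief reduced for at least 6 to 24 hours; do not combine | Yes |
| Thyroid replacement | No interaction reported | Dose may need lowering, with regular tests | Yes, but exclusion 4 removes these patients |

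The caveat in the safety section concerns interactions not yet studied. Those in the right-hand column are already described, so the caveat does not cover them.

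**Step 2: what covers an opioid that starts on treatment?**

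| Provision | Where | What it does | What it leaves open |
|---|---|---|---|
| Exclusions 10 and 21 | Exclusion criteria | Remove current opioid users and planned procedures | Unplanned use after entry |
| Pain-medication question | Baseline Evaluation | Records the past month | Baseline only |
| Two-week call | Follow-up Schedule; Study procedures | Asks about bladder diary, adherence, adverse effects | A new prescription is not itself an adverse effect |
| Pain medication diary | Outcome measures, item 2i | Could record an opioid | Absent from the visit schedule and appendix list; triggers no action |
| Epic entry | Study procedures | Alerts other providers | Gives participant and staff no instruction |
| Discretionary withdrawal | Withdrawal criteria; Procedures for early withdrawals; Reasons for withdrawals | Staff or a provider may withdraw anyone | Does not name opioid use |
| Team discussion of adverse events | Interim analyses | Considers whether continuing is safe | Needs an adverse event to be reported |
| Advice to stop 24 hours ahead | Background and Significance | Covers scheduled procedures | Background only; exclusion 21 already removes those known at entry |

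Several provisions could catch a new opioid. None says what to do about it.

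**Step 3: how much of treatment follows the last scheduled contact?** Treatment lasts 6 × 7 = 42 days and the call comes after 2 × 7 = 14. The remaining 42 − 14 = 28 days are at two capsules nightly (4 mg in the LDN arm). The body text schedules no contact in them before the six-week visit, so a question at the call cannot replace an instruction given at enrollment.

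**Step 4: which duration should an instruction use?** Background and Significance gives two. Receptor blockade is put at 4 to 6 hours; reduced pain relief is put at 6 to 24 hours or longer. The second is the one a prescriber needs.

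**The case against.** The strongest reply is that the safety sentence is a loosely worded literature summary, not permission to use opioids. Its neighbor calls the evidence thin, and the concomitant-medication paragraph names opioid dependence as a contraindication just before its own reassurance. Anyone who reads the whole protocol meets the overdose warning twice. Entry exclusions remove the obvious cases, the withdrawal reasons are an open list under general discretion, and the blind can be broken by a call to the pharmacy after an adverse event. Much of this stands, and it is why the point is minor. It does not make the sentence correct, and general discretion is not a rule for a situation the protocol itself calls dangerous.

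A second reply is that the consent form and the two-week phone script are listed under Appendices but not shown. That also stands. A reader might infer that participants are never warned or asked about opioids; the documents do not support this, because those papers may do both.

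Three further inferences go too far:

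- That the thyroid discrepancy endangers participants. Users of thyroid replacement are excluded, so it has no live consequence.
- That staff are not told of the overdose risk. They are, in Background and Significance and in the risk section.
- That the risk can be put at roughly one chance in eight. Summaries of studies conducted to date describes a six-month LDN pilot in multiple sclerosis where 5 of 40 left, for five listed reasons that include opioid use. Reading that as 1 of 40 over 26 weeks, the six-week rate is 1 − (1 − 0.025)^(6/26) = 0.58%. The chance of at least one among 22 on LDN is then 1 − (1 − 0.0058)^22, about 12%, and the exact 95% interval on 1/40 carries this from 0.3% to 51%. That is one event in another disease, counting any opioid use. It does not measure overdose or other harm and should not be used as if it did.

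**Conclusion.** The conflict over opioids is real and stands in the current text. The visible body text also lacks a specific rule for an opioid needed or started during the six weeks. Severity is minor: the population at risk is narrowed by the exclusions, several general safeguards exist, and the likelihood of harm cannot be estimated from the documents.

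No effect on the efficacy estimate is claimed. The case for acting rests on the seriousness that the protocol itself attaches to the combination and on how little the change costs. It assumes only that unplanned opioid use is possible in a pain population over 42 days. The conclusion about the missing rule is limited to the body text and could be partly answered by the appendices. The conclusion about the safety sentence does not depend on them.

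**What to change.** 1. Replace the sentence under Expected AEs/toxicities with one that names reduced opioid pain relief, and the overdose risk from taking extra opioid to overcome it, as known risks. Have the concomitant-medication paragraph refer to it.
2. Add one rule, the same in both arms so that it can be applied blind. A participant who needs or starts an opioid stops study drug, calls staff, and tells the prescriber that pain relief may be reduced for 6 to 24 hours or more after the last dose. The participant stays in the study and week-6 outcomes are still collected, in keeping with the intention-to-treat analysis.
3. Check the phone script and consent form. If they do not already do so, ask about new opioid use at the two-week call and give the instruction in item 2 at enrollment, which also covers the 28 days after the call.

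The cost is wording changes and a few minutes at contacts that already exist, with no extra visit. Rarely, a participant will stop dosing early.
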